6.6.1.2. TEAEs by System Organ Class and Preferred Term

The following summary tables of TEAEs will be provided by SOC and PT using frequency counts and percentages (i.e. number and percentage of subjects with an event):

- All unsolicited TEAEs
- All unsolicited TEAEs that are treatment-related
- All serious AEs
- All serious AEs that are treatment-related
- All unsolicited TEAEs leading to discontinuation from study vaccine
- All unsolicited TEAEs leading to discontinuation from participation in the study
- All unsolicited severe TEAEs
- All unsolicited severe TEAEs that are treatment-related
- All unsolicited AEs that are medically-attended

Summary tables of all unsolicited TEAEs, Serious AEs, treatment-related SAEs, MAAEs, and TEAE leading to discontinuation from participation in the study will be also be provided by SOC and PT for the Overall Stage

6.6.1.3. TEAEs by Preferred Term

The following summary tables of TEAEs will be provided by PT sorting by frequency on the mRNA-1273 group:

- All unsolicited TEAEs

6.6.1.4. TEAEs by Toxicity Grade

The following summary tables of TEAEs will be provided by the maximum Toxicity Grade using frequency counts and percentages:

- All unsolicited TEAEs

- All unsolicited TEAEs that are treatment-related

6.6.1.5. Subgroup Analysis of TEAEs

An overview of TEAE, TEAE summaries presented by SOC and PT will be provided for the following subgroups:

- Age group (<65, and ≥ 65 years)
- Sex (male, female)
- Baseline SARS-CoV-2 status

These summaries may be provided for subgroups of select baseline characteristics.

6.6.1.6. Summary of AEs in Part B at the Final Analysis of Blinded Data

In Part B, for participants who were randomized to Placebo and requested mRNA-1273, SAE, MAAEs, and AE leading to withdrawal are collected throughout Part B.

At the time of the final analysis of blinded data (from the blinded phase of the study) (Section 6.4.3), in addition to the planned analysis of safety for the blinded phase (Part A), summary of SAE, MAAEs, and AE leading to withdrawal in Part B may be provided. The summary will be provided using the Part B groups during the Part B analysis period for safety as described in the table below.

Table 5: Part B groups and analysis period for safety

Part B Cohort	Description	Part B Analysis Period for Safety
mRNA-1273	Participants received at least one dose of mRNA-1273 in the Blinded Phase	From PDV/unblinding to earlier (data cutoff date for safety, last observed in Study). If a participant received mRNA-1273 in Part B, from 1 st date of study IP in Part B to earlier date of (data cutoff date for safety, last observed in Study).
Placebo	Participants only received Placebo in the Blinded Phase and did not receive mRNA-1273 in Part B	From PDV/unblinding to earlier date of (data cutoff date for safety, last observed in Study)

Placebo-mRNA-1273	Participants only received Placebo in the Blinded phase and received mRNA-1273 in Part B	From first dose of mRNA-1273 in Part B to earlier date of (data cutoff date for safety, last observed in Study)
-------------------	--	---

6.6.2. Solicited Adverse Reactions

An AR is any AE for which there is a reasonable possibility that the test product caused the AE. The term “Solicited Adverse Reactions” refers to selected signs and symptoms occurring after injection administration during a specified post-injection follow-up period (day of injection and 6 subsequent days). The solicited ARs are recorded by the subject in eDiary. The occurrence and intensity of selected signs and symptoms is actively solicited from the subject during a specified post-injection follow-up period (day of injection and 6 subsequent days), using a pre-defined checklist in the eDiary (i.e. solicited ARs).

The following local ARs will be solicited by the eDiary: pain at injection site, erythema (redness) at injection site, swelling/induration (hardness) at injection site, and localized axillary swelling or tenderness ipsilateral to the injection arm.

The following systemic ARs will be solicited by the eDiary: headache, fatigue, myalgia (muscle aches all over the body), arthralgia (aching in several joints), nausea/vomiting, body temperature (potentially fever), and chills.

The solicited ARs will be graded based on the grading scales presented in Table 4 in the protocol, modified from the Toxicity Grading Scale for Healthy Adult and Adolescent Volunteers Enrolled in Preventative Vaccine Clinical Trials ([DHHS 2007](#)). Investigator will assess the Grading for Grade 4 events (with exception of fever).

If a solicited local or systemic AR continues beyond 7 days post injection, the subject will be prompted to capture solicited local or systemic AR in the eDiary until resolution.

All solicited ARs (local and systemic) will be considered causally related to injection.

Analyses of solicited ARs will be provided by treatment group for each injection (first or second) based on the associated subset of Solicited Safety Set, i.e. First (Second) Injection

Solicited Safety Set; and for any injection based on the Solicited Safety Set, unless otherwise specified.

The number and percentage of subjects who reported each individual solicited local AR (has a severity grade of Grade 1 or greater) and solicited systemic AR (has a severity grade of Grade 1 or greater) during the 7-day follow-up period after each injection will be provided by severity grade. The number and percentage of subjects who reported each individual solicited AR will also be summarized by severity grade, days of reporting and injection.

The number and percentage of subjects experiencing fever (a temperature greater than or equal to 38.0°C/100.4°F by the oral, axillary, or tympanic route) by severity grade and the number and percentage of subjects experiencing a fever of Grade 3 or higher temperature (a temperature greater than or equal to 39.0°C/102.1°F by the oral, axillary, or tympanic route) will be provided.

A two-sided 95% exact CI using the Clopper-Pearson method will be provided for the percentage of subjects who reported any solicited local AR, solicited systemic AR, or any solicited AR.

The onset of individual solicited AR is defined as the time point after each injection at which the respective solicited AR first occurred. The number and percentage of subjects with onset of individual solicited AR will be summarized by study day relative to the corresponding injection (Day 1 through Day 7).

The number of days will be calculated as the days of the solicited AR is reported within the 7 days of injection including the day of injection, no matter it is intermittent or continued. If the solicited AR continues beyond 7 days, the consecutive days a solicited AR is reported after 7 days will be included (e.g. an event that lasted 5 days in the first 7 days post injection and 3 consecutive days beyond 7 days post injection, the duration will be reported as 8 (5+3) days.)

All solicited ARs that continue beyond 7 days post injection will be summarized.

The above analyses of solicited ARs will be provided for the following subgroups:

- Age group (<65, and \geq 65 years)
- Sex (male, female)
- Baseline SARS-CoV-2 status

These summaries may be provided for subgroups of select baseline characteristics.

6.6.3. Vital Sign Measurements

Vital sign measurements, including systolic and diastolic blood pressures, heart rate, respiratory rate, and body temperature, will be presented in a data listing. The values meeting the toxicity grading criteria will be flagged in the data listing. The abnormalities meeting the toxicity grading criteria (Grade 2 or higher) in any vital sign measurement will be listed separately. If a subject has a vital sign result with Grade 2 or higher abnormality at any post injection visit, then all results of vital sign measurement for that subject will be presented in the listing.

Observed values and changes from baseline for all vital sign measurements will be summarized at each visit by baseline SARS-CoV-2 serostatus and treatment group as defined in [Section 6.1](#). Shift from baseline in the toxicity grades may be summarized at each visit by treatment group.

In addition, summary of pregnancies and outcome will be provided by treatment group. A listing of pregnancies including outcome will be provided.

6.7. Immunogenicity Analysis

There are two objectives on immunogenicity in this study: to characterize the immunogenicity of mRNA-1273 (secondary objective) and to assess correlates of risk and protection (exploratory objective).

This SAP includes analyses of immunogenicity data for the secondary immunogenicity objective: To evaluate the immunogenicity of 2 doses of mRNA-1273 given 28 days apart.

The analysis of assessing correlates of risk and protection will be included in a separate Immune Correlates SAP.

[figure not shown]
6.7.1. Sampling of the Immunogenicity Subset (Case-cohort Sampling Design)

For characterizing immunogenicity of the vaccine, and for assessing correlates of risk and protection (CoR/CoP), a case-cohort sampling design will be used for measuring bAb and nAb data from a randomly sampled subset of trial participants [the case-cohort Immunogenicity Analysis Set (ccIAS)], or Immunogenicity Subset. The ccIAS cohort consists of a stratified random sample of trial participants (Random SubCohort), augmented with a subset of all primary endpoint cases and SARS-CoV-2 infection endpoint cases. The immunogenicity samples of the ccIAS cohort will be processed and the immunogenicity data will be available for the ccIAS cohort.

A case-cohort sampling design (Prentice (1986)) is used for measuring antibody markers in a random sample of study participants and from all or a subset of cases of COVID-19 primary endpoint (COV-DIS) and infection endpoint (COV-INF) (Figure 3). The random sample is stratified by the key baseline characteristics: assigned treatment arm, baseline SARS-CoV-2 status (defined in Section 6.1), stratification factor used for randomization, and minority (defined as Race being Blacks or African Americans, American Indians or Alaska Natives, Native Hawaiians, and other Pacific Islanders; or Ethnicity being Hispanics or Latinos).

This design uses a stratified random sample instead of the simple random sample proposed by Prentice (1986), the design may also be referred to as a two-phase sampling design, where “phase one” refers to variables measured in all participants and “phase two” refers to variables only measured in a subset (thus the “case-cohort sample” constitutes the phase-two data, e.g. antibodies).

Figure 3: Case-cohort sampling design: participants selected into the stratified random sample (Random Subcohort) and in all or a subset of COVID-19 and COV-INF cases occurring outside of the Random Subcohort.

The Immunogenicity Subset will be used to characterize immunogenicity of mRNA-1273, and to assess correlates of risk and protection. The analysis of characterizing immunogenicity of mRNA-1273 is included in Section 6.7 of this SAP; the analysis of assessing correlates of risk and protection will be included in a separate Immune Correlates SAP.

Eligibility criteria for Immunogenicity SubSet

For stratified random sample:

Only participants in the FAS Set with non-missing key baseline characteristics for the strata, and with serum samples available at both Day 1 (baseline) and Day 57 are eligible for sampling into the stratified random sample (Random Subcohort).

Adjudicated COVID-19 cases and COV-INF cases:

Correlates of Risk (CoR) and Correlates of Protection (CoP) analysis will be documented in a separate Immune Correlates SAP. For CoR/CoP analysis, adjudicated COVID-19 primary endpoint cases (section 6.3.1.1) regardless of baseline SARS-CoV-2 status,

infection cases on mRNA-1273 regardless of baseline SARS-CoV-2 status, and adjudicated COVID-19 cases and infection cases on Placebo in participants with baseline positive SARS-CoV-2 status are eligible to be included regardless of the time of their event date.

Sample size for the stratified random sample (Random Subcohort)

Table 6 describes the numbers of participants sampled into the stratified random sample (Random Subcohort), for each of the 24 sampling strata defined by randomization arm, baseline SARS-CoV-2 status, stratification factor used for randomization (Age \geq 18 and < 65 years and not at risk, \geq 18 and < 65 years and at risk 18-64 not ‘at risk’, Age \geq 65), and minority status. Participants are randomly sampled into the Random Subcohort within each of the strata. This sampling design enables characterization immune response (bAb and nAb readouts) in all relevant subgroups. The sampling is implemented without replacement. A sampling list for the Random Subcohort was planned to be generated after all baseline characteristics for the strata were available and most of the participants have completed the Day 57 visit or discontinued the study.

Table 6 summarizes the size of the Random Subcohort, by baseline factors used to stratify the random sampling. For each of the mRNA-1273 and placebo arms, if any of the 6 baseline SARS-CoV-2 positive strata have fewer than 60 participants enrolled such that it is not possible to sample 60 participants, then all participants in the stratum will be sampled.

Table 6: Random Subcohort Sample Sizes by Baseline Strata

	Baseline SARS-CoV-2 Negative (Total N=1224)						Baseline SARS-CoV-2 Positive (Total N=720)					
Baseline Covariate Strata ¹	1	2	3	4	5	6	1	2	3	4	5	6
Planned Evaluable participants (Total N=1620)												
mRNA-1273	150	150	150	150	150	150	50	50	50	50	50	50

Placebo	20	20	20	20	20	20	50	50	50	50	50	50
Adjusting for approximately 15% participants who may be excluded from the Per-protocol Subcohort for immunogenicity (Total N=1944)												
mRNA-1273	180	180	180	180	180	180	60	60	60	60	60	60
Placebo	24	24	24	24	24	24	60	60	60	60	60	60

1 = ≥ 18 and < 65 years and not at risk, Minority; 2 = ≥ 18 and < 65 years and at risk, Minority; 3 = Age ≥ 65 , Minority; 4 = ≥ 18 and < 65 years and not at risk, non-Minority; 5 = ≥ 18 and < 65 years and at risk, non-Minority; 6 = Age ≥ 65 , non-Minority

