6.2.1.1. Stratification

Randomization in Part A, Blinded Phase of the study will be stratified based on age and, if they are < 65 years of age, based on the presence or absence of risk factors for severe illness from COVID-19 based on CDC recommendation as of March 2020 ([CDC 2020b](#)). There will be 3 strata

for randomization: ≥ 65 years, < 65 years and categorized to be at increased risk (“at risk”) for the complications of COVID-19, and < 65 years “not at risk.” Risk will be defined based on the study participants’ relevant past and current medical history. At least 25% of enrolled participants, up to 50%, will be either ≥ 65 years of age or < 65 years of age and “at risk” at Screening.

Participants who are < 65 years old will be categorized as at risk for severe COVID-19 illness if they have at least 1 of the following risk factors at Screening:

- Chronic lung disease (eg, emphysema and chronic bronchitis), idiopathic pulmonary fibrosis and cystic fibrosis) or moderate to severe asthma
- Significant cardiac disease (eg, heart failure, coronary artery disease, congenital heart disease, cardiomyopathies, and pulmonary hypertension)
- Severe obesity (body mass index ≥ 40 kg/m²)
- Diabetes (Type 1, Type 2, or gestational)
- Liver disease
- HIV infection

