4.4. Randomization

Approximately 30,000 participants will be randomly assigned in 1:1 ratio to receive either mRNA-1273 100 µg or placebo. The randomization will be in a blinded manner using a centralized Interactive Response Technology (IRT) at the Day 1 visit, in accordance with pre-generated randomization schedules. Participants will be stratified by age (≥ 18 and < 65 , or ≥ 65 years) and, if they are < 65 years of age, based on the presence or absence of risk factors for severe illness from COVID-19 based on recommendation by the US Centers for Disease Control and Prevention (CDC) as of March 2020. There will be 3 strata for randomization:

- ≥ 18 and < 65 years and not at risk
- ≥ 18 and < 65 years and at risk
- ≥ 65 years

At least 25% of enrolled participants, but not to exceed 50%, will be from the ≥ 65 years age group and < 65 years at risk group.

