5.5. Immunogenicity Subset and Analysis Populations for Immunogenicity

For characterizing immunogenicity of the vaccine, and for assessing correlates of risk and protection, a case-cohort sampling design will be used for measuring bAb and nAb data from a randomly sampled subset of trial participants [the case-cohort Immunogenicity Analysis Set (ccIAS)], or Immunogenicity SubSet. The ccIAS cohort consists of a stratified random sample of trial participants (Random SubCohort), augmented with a subset or all primary endpoint cases and SARS-CoV-2 infection endpoint cases. The immunogenicity samples of the ccIAS cohort will be processed and the immunogenicity data will be available for the ccIAS cohort. The Immunogenicity Subset consists of all

participants in the ccIAS who had a valid baseline immunogenicity test result (prior to the first injection of IP) and at least one valid post-baseline result.

The analysis of characterizing immunogenicity of mRNA-1273 is included in Section 6.7 of this SAP, the primary analysis population to characterize immunogenicity of mRNA-1273 is the Per-Protocol Random Subcohort for Immunogenicity (Section 6.7.2); the analysis of assessing correlates of risk and protection will be included in a separate Immune Correlates SAP. Details of the case-cohort sampling, and analysis populations for characterizing immunogenicity of mRNA-1273 are also included in Section 6.7 of this SAP.

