- Reverse cumulative distribution function curve (RCDF) at each time point. The number and percentage of subjects with fold-rise ≥ 2 , fold-rise ≥ 3 , and fold-rise ≥ 4 from Baseline at each post injection time points will be tabulated with 2-sided 95% Clopper Pearson CIs. If assay-specific fold rise criteria are available, the number and percentage of subjects with fold-rise exceeding the criteria with 95% CI will be provided instead.
- Proportion of subjects with seroconversion due to vaccination will be tabulated with 2-sided 95% Clopper-Pearson CIs at each post-baseline timepoint. Seroconversion due to vaccination at a subject level may be defined as a change from below the LLOQ to equal to or above LLOQ, or 4-fold rise if baseline is equal to or above LLOQ. The definition of seroconversion may depend on assay-specific performance characteristics and the final definition of seroconversion due to vaccination will be documented in a memo.

The GMT and GM levels will be calculated using the following formula:

$$10^{\left\{ \frac{\sum_{i=1}^n \log_{10}(t_i)}{n} \right\}}$$

where t_1, t_2, \dots, t_n are n observed immunogenicity titers or levels.

The geometric mean fold rise (GMFR) measures the changes in immunogenicity titers within subjects. The GMFR will be calculated using the following formula:

$$10^{\left\{ \frac{\sum_{i=1}^n \log_{10} \left(\frac{v_{ij}}{v_{ik}} \right)}{n} \right\}} = 10^{\left\{ \frac{\sum_{i=1}^n \log_{10}(v_{ij}) - \log_{10}(v_{ik})}{n} \right\}}$$

where, for n subjects, v_{ij} and v_{ik} are observed immunogenicity titers or levels for subject i at time points j and $k, j \neq k$.

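### Overall GMT, GMFR and seroresponse in the Random Subcohort are unweighted although strata are sampled at unequal rates, so they describe an equal-strata mix and not the enrolled mix

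*SAP*

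**What the plan says.** The Part A SAP, Section 6.7.1, describes a stratified random sample with 24 strata: arm, baseline SARS-CoV-2 status, the three randomization strata, and minority status. "Participants are randomly sampled into the Random Subcohort within each of the strata", without replacement. Table 6 sets the numbers. In each arm and serostatus group they are the same for all six covariate strata: 180 per stratum for baseline-negative vaccinees, 24 for baseline-negative placebo participants, and 60 for baseline-positive participants in either arm. The section says that the design lets the immune response be characterized in all relevant subgroups, and it calls the design two-phase.

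On who is analysed, Section 5.5 states that "the primary analysis population to characterize immunogenicity of mRNA-1273 is the Per-Protocol Random Subcohort for Immunogenicity (Section 6.7.2"). On the estimator, Section 6.7.4 says "The GMT and GM levels will be calculated using the following formula", and what follows is ten to the power of the simple mean of the log10 values. GMFR has the same form. Intervals for both come from the t-distribution of the logs. Seroresponse (there called seroconversion due to vaccination) is a plain proportion with a Clopper-Pearson interval. The Part B and C SAP repeats the GMT and GMFR formulas in its appendix. The immunogenicity sections of both SAPs and Protocol 9.5.3 contain no sampling weight, no design-based variance and no standardization to enrolled shares.

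On the enrolled mix, Protocol 6.2.1.1 says "At least 25% of enrolled participants, up to 50%, will be either ≥ 65 years of age", or younger and at risk. SAP Section 4.4 gives the same limits.

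**The concern.** A sample with equal numbers per stratum is a good design for describing each stratum. A plain mean over that sample, however, gives every stratum the same influence, however many participants it represents. The overall GMT equals the enrolled-population GMT only if the titers do not differ between strata.

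The secondary immunogenicity objective is to evaluate two doses of the vaccine, and its endpoints are arm-level GMT and GMFR. A reader will naturally take the overall figure as describing the people who were enrolled. Absolute levels from this trial also serve as a reference elsewhere: Protocol 2.2.2 and 4.3 express a booster response in another study as a multiple of the post-primary peak in this one (without saying which estimate of that peak was used). Such comparisons depend on the mix of participants. The sampling fractions are known to the sponsor, so the mismatch can be removed.

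**Working it through.** **The plan's own figures.** Planned evaluable: 6 × 150 + 6 × 20 + 12 × 50 = 1620, as stated. Sampled: 6 × 180 + 6 × 24 = 1224 baseline-negative and 12 × 60 = 720 baseline-positive, together 1944, as stated. The inflation factor is 1944/1620 = 1.2, an exclusion of 16.7%, which fits the SAP's approximate 15%. Table 6 reproduces.

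**Share of high-risk participants.** Here high-risk means aged 65 or over, or under 65 and at risk. Four of the six equal strata are high-risk, so their sample share is 4/6 = 66.7%. Let w be their share of the trial, 0.25 to 0.50 by the enrolment limits (assuming that baseline-negative participants follow the same mix).

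**Relative sampling rate**, high-risk to not at risk: (0.667/w) ÷ (0.333/(1 − w)) = 2(1 − w)/w.
- w = 0.50: 2 × 0.50/0.50 = 2.0
- w = 0.25: 2 × 0.75/0.25 = 6.0

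Minority participants are three of six strata, 50% of the sample. The documents do not give their trial share.

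**Distortion of the GMT.** Let r be the ratio of GMTs, high-risk to not at risk. On the log scale the unweighted mean gives high-risk participants weight 2/3 instead of w, so unweighted GMT ÷ population-weighted GMT = r^(2/3 − w). No r is given in the documents, so the values below are assumptions.

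| r | w = 0.50 | w = 0.25 |
|---|---|---|
| 1.0 | 1.000 | 1.000 |
| 0.9 | 0.983 | 0.957 |
| 0.8 | 0.963 | 0.911 |

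The overall GMT is thus about 2-4% low at r = 0.9 and 4-9% low at r = 0.8. The direction also depends on r being below 1. A difference by minority status would act separately: with a minority to non-minority ratio of 1.25 and a trial share of 40% or 20% (both assumed), 1.25^(0.5 − share) gives 1.023 or 1.069, which is in the opposite direction.

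**Precision cost of weighting.** The Kish design effect for six equal-sized samples is 6 × Σs², where s is each stratum's population share. It assumes similar titer variance across strata. I also assume that minority status is independent of risk and that the high-risk group splits equally between its two strata.
- w = 0.50, minority 40%: shares 0.20, 0.10, 0.10, 0.30, 0.15, 0.15; Σs² = 0.195; design effect 1.17
- w = 0.25, minority 20%: shares 0.15, 0.025, 0.025, 0.60, 0.10, 0.10; Σs² = 0.404; design effect 2.42

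Interval width grows by the square root: 1.08 to 1.56, or 8-56% wider. The 900 evaluable baseline-negative vaccinees then carry the information of about 770 down to 370.

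**Do the planned models restore the mix?** The MMRM and ANCOVA (SAP 6.7.5) adjust for randomization stratum and may adjust for minority. No population margins are specified. Default least-squares means give the three randomization strata equal weight, which is again two-thirds high-risk.

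**Serostatus.** Baseline-positive participants are 360 of 1440 sampled vaccinees (25%) and 360 of 504 sampled placebo participants (71%). This matters only if serostatus groups are pooled. Protocol 9.5.3 plans results by serostatus, and the MMRM is run separately by serostatus. The risk and minority imbalance remains within each group.

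**The case against.** The strongest reply is that no estimand is missed. Neither SAP says that the overall GMT is meant to describe the enrolled mix. Equal strata were chosen for subgroup description, and the enrolled mix is itself shaped by a quota. This stands in part: the design is sound, and stratum estimates need no correction. It does not settle which population the overall figure describes, and the SAP is silent on that. Elsewhere the SAP does weight strata by their empirical share, in the covariate-adjusted cumulative incidence analysis of Section 6.8.6, so the idea is not foreign to the plan.

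A reader might infer that the booster noninferiority comparison rests on a distorted Day 57 benchmark. The documents do not support that. The Part B and C SAP, Section 5.5.3.2, describes a within-participant GMT ratio, so the same people stand on both sides. The alternative uses a historical control drawn from the same per-protocol Random Subcohort as the booster set (Section 4.3), adjusted for age group. The seroresponse comparison is also paired where feasible.

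A reader might also infer a large bias. A 19% shortfall follows from the same formula, but only at r = 0.6 together with w = 0.25 (0.6^0.417 = 0.81). Nothing in the documents supports such a ratio. The one relevant statement, in Protocol 2.2.2, is that the Phase 1 neutralizing response at 100 µg was similar across age groups. That evidence is small and concerns age only, but it points to r near 1.

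Finally, weighting cannot recover the whole trial population. Sampling required serum at Day 1 and Day 57, and the analysis set then applies per-protocol exclusions. This stands and limits what the weighted figure may be said to describe.

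**Conclusion.** The point holds as a modest one. The unequal sampling rates, 2- to 6-fold by risk group, follow from Table 6 and the enrolment limits, provided baseline-negative participants follow the enrolment mix. The absence of weights is plain from Section 6.7.4. The overall arm-level GMT, GMFR and seroresponse therefore refer to an equal-strata mix, and neither reporting by serostatus nor model adjustment changes that.

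The size cannot be fixed from the documents. On assumed GMT ratios of 0.9 and 0.8 the overall GMT would be about 2-4% and 4-9% low; with no difference between strata it would not be off at all. The vaccine-versus-placebo conclusion, the stratum-specific results and the Part C booster comparison are not materially affected. This is a cheap improvement in what the overall numbers mean, and it does not threaten any conclusion.

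**What to change.** Within each baseline serostatus group, add overall GMT, GMFR and seroresponse in which each participant is weighted by the stratum's size in the eligible set divided by the number sampled from it. Use design-based standard errors in place of the simple t and Clopper-Pearson intervals. If only a subset of the planned Random Subcohort is assayed, as Section 6.7.2 allows, the divisor should be the number in that subset. Show these beside the unweighted and stratum-level values. State that the weighted figures refer to the eligible per-protocol population, and that the unweighted ones refer to the sampled mix.

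The cost is some programming and wider intervals for the overall estimate, about 8-56% on the assumptions above. The Part B and C SAP (Sections 3.2.2 and 5.5) records that Part A immunogenicity has already been reported, so this would be a supplementary analysis that leaves the reported results in place.
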